Existing RAF inhibitors have selective anti-mutant BRAF activity, i.e. in tumour cells harbouring the BRAF mutation they effectively block BRAF activity, terminating pathway signalling. In BRAF wild type cells, or in cells where aberrant signalling is mediated by oncogenic RAS, the use of selective BRAF inhibition promotes MAPK signalling rather than inhibiting it¹⁶. Several theories exist regarding the mechanism for this, but all essentially describe the formation of heterodimers between BRAF and CRAF, the consequent transactivation of CRAF, and promotion of MAPK pathway signalling. Inhibitors effective against BRAF and CRAF ensure that both RAF isoforms are equally inhibited, preventing transactivation and thus terminating MAPK pathway signalling. This means that not only are mutant BRAF driven cancers inhibited, but additionally that mutant RAS-driven malignancies can also be treated, without the development of skin toxicities seen previously with selective RAF inhibitors. A panel of panRAF inhibitors has been developed by the ICR to exploit these observations for therapeutic gain; this trial aims to assess the safety and tolerability of the most promising of these inhibitors, CCT3833, in humans.

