2 TRIAL DESIGN

2.1 Clinical trial design

This is a first-in-human, open-label, Phase 1 trial of CCT3833 in patients with advanced solid malignancy. The trial will be conducted in two parts; an initial dose escalation phase (Part A), followed by an expansion stage (Part B, with three cohorts), wherein patients will be treated at the recommended Phase 2 dose, to further define tolerability and evaluate safety in a larger population and to support the design of subsequent trials with CCT3833 (see Table 4).

Part A, the dose escalation stage, will aim to establish the maximum dose that can safely be delivered to man, and establish what toxicities may arise. Patients with all-solid tumours will be recruited to this stage of the study, with no mandatory oncogene mutation sequencing being performed. As there is no evidence that panRAF inhibitor

therapy in the absence of specific oncogene mutations has deleterious effects, exclusion/inclusion of patients on this basis is felt to be unnecessary in the dose escalation stage. This will however be mandated (alongside a diagnosis of melanoma) in Part B, the dose expansion stage, and will be used to define the three cohorts of melanoma patients.

The starting dose for the first cohort in Part A is 20 mg. The bioanalysis of the PK samples from at least the first two patients in each cohort will be made available prior to dose escalation procedures. The dose escalation decision will be made on the basis of PK, safety, and tolerability of the dose after 3 patients have completed one 28-day cycle. Patients will continue with treatment until disease progression or failure to tolerate treatment. These patients will follow the treatment schedule provided in section 8.1 and Table 14.

Part B, the dose expansion stage, will further investigate the safety, tolerability, and early efficacy signals in BRAF- or RAS-mutant melanoma patients. The dose for Part B will be the recommended Phase 2 dose, selected based on the MTD and other data derived from Part A, the dose escalation phase. There will be 3 patient cohorts, defined by mutation and treatment history. All cohorts will receive the same dose for up to 12 months, or until disease progression. These patients will follow the treatment schedule provided in section 8.2 and Table 15.

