- AE evaluation.
- Concurrent medications.
- ECOG performance status (Appendix 2) and weight.
- Physical examination.
- Intensive monitoring of vital signs will take place during the single dose PK admission between Day -7 and Day -3. During this admission, measurement will be taken:
 - Before dosing.
 - Every 30 minutes for 4 hours post dosing.

- Single standard ECGs will be conducted timed to coincide with the expected T_{\max} (e.g. 4 hours post-dose and 24 hours post-dose).

8.1.2.2 *Safety and tolerability assessments*

Clinical review

Patients will be clinically reviewed on a weekly basis (± 1 day) starting from Cycle 1, Day 1. The reviews will be repeated on a weekly basis (± 1 day) (i.e. Cycle 1 Days 8, 15, and 22; Cycle 2 Days 1, 8, 15, and 22) until 8 weeks follow-up have been completed. If no DLTs are encountered, the visit frequency will be reduced to fortnightly (± 1 day), for a further 8 weeks (i.e. Cycle 3 Days 1 and 15; Cycle 4 Days 1 and 15). Again if no further DLTs are observed, the visit frequency will be reduced to every 4 weeks (± 1 day) (i.e. Cycle 5 Day 1, Cycle 6 Day 1, etc.) until disease progression.

Physical examination

A complete physical examination (including skin review) should be performed on Day 1 (± 1 day) of each study cycle, and at the end of treatment. Additional examinations may be performed at the Investigator's discretion, if clinically indicated.

Weight

This will be measured on Day 1 (± 1 day), of each cycle and at the end of treatment.

Vital signs

Intensive monitoring of vital signs (temperature, pulse, blood pressure and oxygen saturation) will take place during the single dose PK admission between Day -7 and Day -3. During this admission, measurement will be taken:

- Before dosing
- Every 30 minutes for 4 hours post dosing

Thereafter vital signs will be measured as per the clinical review schedule outlined above, and at the Off-study visit.

Laboratory evaluations

Full haematological and biochemical analysis, as described for baseline, should be performed as per the clinical review schedule (± 1 day):

- Cycle 1-2 Days 1, 8, 15, and 21.
- Cycle 3-4 Days 1 and 15.
- Cycle 5 Day 1 and Day 1 only of all subsequent cycles (assuming no DLTs encountered in expansion phase).
- End of treatment (± 3 days).

ECG

Single standard ECGs will be conducted during the single dose PK admission timed to coincide with the expected T_{max} (e.g. 4 hours post-dose and 24 hours post-dose).

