Blood for PK assays ¹			x				x (C2D1)				
----------------------------------	--	--	---	--	--	--	----------	--	--	--	--

- a) Radiological assessment using CT or MRI as appropriate.
- b) If the patient is a woman of child bearing potential.
- c) Tumour tissue needle biopsies (10mg material required) for pharmacodynamics assessment will be optional for patients in Part A (dose escalation stage). The sampling timepoints will be pre-dose between Day -28 and the first dose for PK between Day-7 and -3 and at C2D1 (± 3 days), and when the patient is withdrawn from treatment.
- d) Research blood samples for circulating tumour cell collection (2-3 x 10mL) will be requested (optional) from patients in Part A (dose escalation stage). The sampling points will be pre-dose between Day -28 and the first dose for PK (between Day-7 and Day -3), at Cycle 2 Day 1 (± 3 days) and thereafter every 2 cycles (i.e. Cycle 4 Day 1, Cycle 6 Day 1 etc), and when the patient is withdrawn from treatment.
- e) Research blood samples for PBMC collection (4-5 x 5ml) will be requested (optional) from patients in Part A (dose escalation stage). The sampling time points will be alongside the PK blood samples: namely pre-dose and following single dose administration (on Day -7 to Day -3) at 4, 8, 24 and 48 hours post-dose, and alongside the PK blood samples on Cycle 2, Day 1 (± 3 days) at 0, 4, 8, 24 hours post-dose.
- f) Complete physical examination to be performed pre-study, then all examinations can be symptom-directed performed on Day 1 of each cycle
- g) Temperature, pulse rate, blood pressure and oxygen saturation rate should be performed pre-dose and then repeated every 30 mins (± 5 min) for the first 4 hours post-dose at the first dose for PK (between Day-7 to -3). Vital signs should be repeated each week of Cycles 1 and 2, and then on D1 and D15 from Cycle 3 onwards at the discretion of the Investigator, and reduced again to once a month from Cycle 5 onwards.

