Clinical disease assessment (if applicable)		x	At end of every cycle				x	
AE evaluation	x		x	x	x	x	x	x ^I
Concurrent medications	x		x	x	x	x	x	
Urinalysis (bHCG) ^B		x						
Tumour serum markers (if applicable)		x	At end of every cycle				x (unless performed within previous 6 weeks)	
Optional tumour biopsy ^C	x				x		x	
Optional CTC/genetics research blood samples ^D	x				x (and every 2 cycles thereafter)		x	
ECOG performance status (Appendix 2)	x	x	x	x	x	x	x	
Physical examination ^E		x	x	x	x	x	x	
Weight		x	x		x	x	x	
Vital signs ^F : temperature, pulse, BP, oxygen saturation		x	x	x	x	x	x	
Laboratory tests ^G		x	x	x	x	x	x	x ^I

ECG		x	x	x	x	x	x	
Echocardiogram ^H (±3 days)	x				x			

- A. Radiological assessment using CT or MRI as appropriate. Baseline assessment to include MRI brain; only to be repeated if evidence of brain metastases at baseline or in response to new symptoms.
- B. If the patient is a woman of child bearing potential
- C. Tumour tissue needle biopsies (10mg material required) for pharmacodynamics assessment will be optional for patients treated in Part B (expansion cohorts). The three sampling points will be pre-dose between Day -28 and C1D1, during treatment on C2D1 (± 3 days), and at disease progression.
- D. Research blood samples for circulating tumour cell collection (2-3 x 10mL) will be requested (optional) from patients in Part B (dose expansion stage). The sampling points will be pre-dose between Day -28 and Cycle 1, day 1, at Cycle 2 Day 1 (± 3 days), and every 2 cycles thereafter (i.e. Cycle 4 day 1, Cycle 6 day 1 etc) and when the patient is withdrawn from treatment.
- E. Complete physical examination to be performed pre-study, then all examinations can be symptom-directed performed on Day 1 of each cycle
- F. Temperature, pulse rate, blood pressure and oxygen saturation rate should be performed at each clinical visit.

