Skin reactions /malignancies	Regular scheduled clinical review and examination (including palms and soles) with referral for dermatology review/treatment of lesions.
Arthralgia	Regular scheduled clinical review and examination.

Myositis	Regular scheduled clinical review and examination; monitoring of blood tests (e.g., CK); referral for further specialist review as necessary.
Alopecia	Regular scheduled clinical review and examination.
Fatigue	Regular scheduled clinical review and examination.
Uveitis/Iritis	Regular scheduled clinical review and examination with referral to Ophthalmology for review of any concerning symptoms.
Vasospasm	Regular scheduled clinical review and examination with referral for further specialist review as necessary.
Slow wound healing	Patients requiring major surgery to be excluded from trial.
Febrile reactions	Clinical observations including temperature measurement.
Haematological abnormalities such as anaemia or thrombocytopenia	Routine haematology blood test monitoring.
Biochemical abnormalities such as altered liver function tests	Routine biochemistry blood test monitoring.
ECG changes eg QTc prolongation	Exclusion of patients with baseline QTc prolongation (> 450 ms). Exclusion of patients with uncontrolled hypertension on > 1 antihypertensive. ECG monitoring of patients during treatment and central analysis of ECGs for any effects on QTc interval, and exclusion of patients if QTc interval becomes > 500 ms.
Left ventricular dysfunction (eg reduced LVEF)	Baseline echocardiography to exclude patients with inadequate LVEF (< 50%). Repeat monitoring with echo at 1 month and thereafter if symptoms of dysfunction develop.
Embryo-fœtal toxicity	Measures to avoid pregnancy as described in section 9.6.
Any signal emerging during clinical study	Ongoing monitoring by the SRC.

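### Table 14 footnote f and Table 15 footnote E allow symptom-directed Day 1 examinations where sections 8.1.2.2 and 8.2.2.1 call for a complete examination with skin review

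*Combined protocol and SAP*

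**What the plan says.** The section text is the same in both parts. Section 8.1.2.2 (Part A) and section 8.2.2.1 (Part B) state: "A complete physical examination (including skin review) should be performed on Day 1" (with a window of ±1 day) "of each study cycle, and at the end of treatment". Only examinations beyond these are left to the investigator's discretion.

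The footnotes to the physical examination rows are also the same in both parts. Table 14 footnote f and Table 15 footnote E read: "Complete physical examination to be performed pre-study, then all examinations can be symptom-directed performed on Day 1 of each cycle".

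Section 2.1 tells sites to use both sources. For Part A: "These patients will follow the treatment schedule provided in section 8.1 and Table 14". For Part B: "These patients will follow the treatment schedule provided in section 8.2 and Table 15". The supplied text contains no rule on which prevails if they differ.

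Table 16 (section 11.3.6) lists skin reactions and malignancies as a potential risk. Its mitigating step is: "Regular scheduled clinical review and examination (including palms and soles) with referral for dermatology review/treatment of lesions".

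**The concern.** Section text and footnote describe the same visit, Day 1 of each cycle, and set different standards for it. Staff who work from the schedule of events could reasonably conclude that a patient with no skin complaint needs no skin examination after baseline.

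For skin, Table 16 offers nothing else by way of detection. Other organ risks in that table have an objective check: creatine kinase for myositis, ECG for QTc, echocardiography for left ventricular function, blood tests for haematology and liver. Some others also rest on clinical review, but arthralgia and fatigue are things a patient reports. An early skin lesion may not be.

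The protocol itself gives reason to look. Section 1.1.1.4 links keratoacanthoma and squamous cell carcinoma to BRAF-targeted therapy, and section 1.2.5 expects a different side-effect profile from panRAF inhibition and promises cautious monitoring. Safety and tolerability is a primary endpoint in both parts (section 10.3), and section 10.3.1 reports toxicity of grades 1 to 4 in Part B, so low-grade skin events count. If the two centres follow different instructions, the recorded frequencies depend partly on how hard each one looked.

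**Working it through.** The protocol gives no figure to reproduce. The check is a comparison of texts, with simple counts for scale.

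**1. The same visit under each instruction**

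| Item | Sections 8.1.2.2 and 8.2.2.1 | Footnotes f and E |
|---|---|---|
| Pre-study | Examination listed at baseline (8.1.1.1, 8.2.1.1) | Complete |
| Day 1 of each cycle | Complete, with skin review | May be symptom-directed |
| End of treatment | Complete, with skin review | No complete examination required |
| Force of wording | *should* | *can* |

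Neither table has an end-of-treatment column. Each has an Off-study column, for a visit 28 days after the last dose. Sections 8.1.3 and 8.2.3 list an examination there without saying that it is complete.

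**2. Can one conduct satisfy both?** Yes. The footnote is a permission, so a complete examination every time complies with both. The converse fails: a symptom-directed Day 1 examination is allowed by the footnote and departs from the section.

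**3. Number of complete examinations after Cycle 1 Day 1, for a patient treated for n cycles**

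- By the text: (n − 1) Day 1 visits + 1 at end of treatment = n. For n = 2, 6 and 12 this is 2, 6 and 12.
- By the footnotes: 0 are mandatory as complete.

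**4. Interval between complete examinations by the text**

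- Nominal: one cycle = 28 days; with the ±1 day windows, 28 + 1 + 1 = 30 days.
- Section 6.9.2 lets a cycle start slip by up to 2 weeks for drug-related toxicity, and removes a patient for other delays only after more than 28 days. If Day 1 moves with the delay, the interval is 28 + 14 = 42 days, or up to 28 + 28 = 56 days, before windows. Section 6.1 says that there are no delays between cycles, so the documents do not settle this. Only the nominal 28 days is firm.

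**5. Duration over which the footnotes require no complete examination.** In Part B, treatment lasts up to 12 cycles (section 6.11): 12 × 28 = 336 days of dosing.

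**6. Other scheduled contact in Cycles 1 and 2**

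- Part A: Days 1, 8, 15 and 22 of two cycles = 2 × 4 = 8 reviews.
- Part B: Cycle 1 Day 1, Cycle 1 Day 15 and Cycle 2 Day 1 = 3 reviews, then monthly.

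**7. Reach of the wording.** Up to 42 patients in Part A plus about 27 in Part B, about 69 in all. This is the number to whom the footnotes apply, not a number harmed.

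**8. Table 14 cells.** As extracted, the physical examination row is blank for Day 1 of Cycles 2 to 4. The weight row has the same blanks, and both section 8.1.2.2 and footnote f cover Day 1 of every cycle. This is at most a table slip, not a lost examination. The flow charts (Tables 12 and 13) are not shown, and nothing is inferred about them.

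**The case against.** The strongest reply is that the documents, read together, already point to the right conduct. Section 2.1 asks sites to follow section and table, and only the complete examination satisfies both. Table 16 separately commits to scheduled examination including palms and soles. Adverse events are evaluated at every scheduled on-treatment visit. Clinical disease assessment is due every 4 weeks and would bring some skin under inspection in melanoma patients. On this view the fault is one of clarity and the safeguard is not lost.

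Much of that stands. The conflict can be reconciled, and it bites only where someone relies on the footnote. But the footnote is an express permission in the document staff use at the visit, and nothing tells them that the section overrides it. The other contacts do not fill the gap: adverse event evaluation specifies no skin examination, and the tables qualify disease assessment as applying only where relevant.

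Three stronger readings are tempting, and the documents do not support them.

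- A reader might infer a 336-day gap between examinations. That figure is the 12-cycle dosing length. Under footnote E there is no second mandatory complete examination to close a gap, and symptom-directed examinations continue.
- A reader might infer that under-ascertainment would falsely confirm the expectation in section 1.1.1.5 that panRAF inhibition works "without the development of skin toxicities seen previously with selective RAF inhibitors". That sentence is background. It is not an objective or endpoint, and section 10.3.1 plans descriptive tables with no skin-specific comparison.
- A reader might infer that the MTD is at risk. It comes from Part A, with weekly review in Cycles 1 and 2, and Table 8 counts a skin event as a DLT only at grade 3 or above persisting for more than 7 days despite optimal treatment. Such an event is unlikely to go unnoticed.

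**Conclusion.** The inconsistency is real and appears in both parts. The sections schedule a complete examination with skin review nominally every 28 days and at end of treatment; the footnotes make none mandatory as complete after baseline. For a patient treated for 12 cycles that is 12 against 0 after Cycle 1 Day 1.

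The consequence is limited to ascertainment of asymptomatic or low-grade skin events, which could be missed, referred late or recorded unevenly between the two sites. It is most plausible in Part B, where scheduled reviews are fewer. It depends on a site using the footnote's permission; a site that examines completely each time is unaffected. The documents give no rate of unreported lesions, so no number of missed events is offered. No effect on DLT counts or the MTD is claimed.

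The point should be corrected because it touches a primary endpoint and a stated risk mitigation, and because an examination not done cannot be recovered at analysis.

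**What to change.** Reword footnotes f and E alike, for example: *Complete physical examination pre-study, and complete physical examination including skin review (with palms and soles) on Day 1 of each cycle and at end of treatment (the Off-study visit if no separate visit is held); examinations at other visits may be symptom-directed.* The Cycle 1 Day 15 examination in Table 15 can then remain symptom-directed.

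If the sponsor did intend symptom-directed general examinations, both sections should be changed instead, with skin review kept mandatory so that Table 16 still holds.

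Marking Day 1 of Cycles 2 to 4 in the Table 14 physical examination row is optional tidying.

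The cost is a minor protocol amendment. Under section 11.1 it still needs agreement from the sponsor, chief investigator, site principal investigators and statistician, then an ethics favourable opinion and MHRA approval if appropriate, so it is best combined with the next amendment. Rewording the footnotes adds no visit and no procedure beyond what sections 8.1.2.2 and 8.2.2.1 already call for.

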9 ASSESSMENT OF SAFETY

9.1 Adverse event definitions

9.1.1 Adverse events

An adverse event (AE) is any untoward, undesired or unplanned occurrence in a patient administered an IMP, a comparator product or an approved drug. An AE can be a sign, symptom, disease, and/or laboratory or physiological observation that may or may not be related to the CCT3833 or comparator.

An AE includes but is not limited to those in the following list:

- A clinically significant worsening of a pre-existing condition. This includes conditions that may resolve completely and then become abnormal again.
- AEs occurring from an overdose of an IMP, whether accidental or intentional.
- AEs occurring from lack of efficacy of an IMP, for example, if the Investigator suspects that a drug batch is not efficacious or if the Investigator suspects that the IMP has contributed to disease progression.

Other reportable events that must be treated as AEs are listed below:

- Pregnancy exposure to the IMP. Any pregnancy occurring in a patient or a patient's partner during treatment with an IMP or occurring within 6 months of the last IMP administration must be reported to the RM-CTU in the same timelines as an SAE. These should be reported even if the patient is withdrawn from the trial.
- Overdose or inadvertent or accidental exposure to an IMP with or without an AE
- Any AE that could be related to the protocol procedures, and which could modify the conduct of the trial.

Underlying disease - Any event(s) considered related to the underlying disease do not require reporting.

9.1.2 Serious adverse events

A serious adverse event (SAE) is any AE, regardless of dose, causality or expectedness, that:

- results in death.
- is life-threatening.
- requires in-patient hospitalisation or prolongs existing in-patient hospitalisation (some hospitalisations are exempt from SAE reporting – see section 9.2.1).
- results in persistent or significant incapacity or disability.
- is a congenital anomaly or birth defect.
- is any other medically important event.

For screening failures, SAEs will be reported to the RM-CTU from the date of consent until the date the patient is confirmed as ineligible. For eligible patients, SAE and AE collection and monitoring commences from the time the patient gives their written consent to participate in the trial and continues for 28 days after the last administration of the IMP.

Follow-up of AEs with a causality of possibly, probably or highly probably related to the IMP will continue until the events resolve, stabilise or the patient starts another anti-cancer therapy.

9.1.3 Determining adverse event causality

The relationship of an AE to the IMP is determined as follows:

Highly probable

- Starts within a time related to the IMP administration and
- No obvious alternative medical explanation.

Probable

- Starts within a time related to the IMP administration and
- Cannot be reasonably explained by known characteristics of the patient's clinical state.

Possible

- Starts within a time related to the IMP administration and
- A causal relationship between the IMP and the AE is at least a reasonable possibility.

Unlikely

- The time association or the patient's clinical state is such that the trial drug is not likely to have had an association with the observed effect.

Not related

- The AE is definitely not associated with the IMP administration.

Note: Drug-related refers to events assessed as possible, probable, highly probable or definitely.

The Investigator must endeavour to obtain sufficient information to determine the causality of the AE (i.e. IMP, other illness, progressive malignancy etc) and must provide his/her opinion of the causal relationship between each AE and IMP. This may require instituting supplementary investigations of significant AEs based on their clinical judgement of the likely causative factors and/or include seeking a further opinion from a specialist in the field of the AE.

